2.4 Design and Procedures

2.4.1 Study Design

This is a prospective, randomized, double-blind, placebo-controlled, cross-over pilot study in 35 evaluable subjects with painful CIPN. If our hypothesis is confirmed, then patients with lower MPT at baseline will have larger analgesic effect with pregabalin than with placebo.

Registration, Randomization, and Blinding

Subjects that meet all criteria and wish to participate will be assigned study ID # and be randomized for the sequence of treatment for the study sessions. Patients may not start any protocol intervention until registration through the Siteman Cancer Center (SCC) is complete. The following steps will be taken before any study interventions occur: 1) confirmation of patient eligibility, 2) registration of patient in the SCC database, and 3) assignment of study ID #.

According to a computer-generated list of randomization numbers, the sequence of interventions will be determined: pregabalin and then matching placebo, or vice versa. Randomization will be performed by blocks of 8 subjects, without stratification. An unblinded

investigator will be assigned to match the study number with randomized treatment sequence, and this person will dispense the study medications. This investigator will not be involved at any stage at patient assessment, data collection or analysis. The participants and all other study personnel will be blinded to the treatment sequence allocation. At the end of the study, the subjects will be asked to complete a participant blinding questionnaire, to assess the risk of possible unmasking. As an additional approach to identify inadvertent failure in randomization or patient allocation, a single blood sample will be obtained at the last visit of each session, to determine the presence of pregabalin in plasma in patients allocated to pregabalin, and lack of drug in the placebo arm.

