2.4.7 Statistical Methods

The primary outcome is the comparison of slopes of the two correlations: baseline MPT vs % pain reduction with pregabalin, and baseline MPT vs % pain reduction with placebo. Percent pain reduction will be assessed from the difference in average pain intensity at baseline and the average daily pain intensity on days 24-28 of each treatment phase, obtained from the patient diaries. The two slopes will be compared using t-test. Significant difference between slopes will indicate that baseline MPT correlates with pregabalin response (vs. placebo response) in painful CIPN, regardless of differences in average pain response between pregabalin and placebo.

As secondary analyses, we will compare mean absolute pain reduction with pregabalin to absolute pain reduction to placebo (both for average daily pain and maximum daily pain), using paired t-test, given normal data distribution. If normal distribution is not obtained, we will use Wilcoxon signed ranked test. In addition, we will perform Fisher exact test to compare the proportion of patients with 50% or more reduction in average pain intensity from baseline with pregabalin vs. placebo. Number needed to treat (NNT) will be calculated from this proportion of responders to pregabalin and placebo. These secondary analyses are aimed at detecting group differences in response to pregabalin vs. placebo.

In exploratory analysis, we will examine the correlations between the various demographical and QST variables (WDT, CDT, HPT, CPT, WSI, TS, CPM) and pain reduction with pregabalin vs placebo, for generating hypotheses for additional predictors of response to pregabalin in CIPN. We will also perform exploratory multiple regression analysis to evaluate how various QST factors perform in combination as treatment response predictors.

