2.4.8 Sample Size

The sample size calculation was performed for detecting a significant difference between correlations on % pain reduction vs. MPT slopes of pregabalin and placebo in linear bivariate regression. Assuming slope and SD data based on our preliminary results of MPT vs. response with another drug, lidocaine (Haroutiunian, Nikolajsen et al. 2013); to detect 0.3 (SD=0.5) difference in correlation coefficients between the two slopes, with 85% power and alpha=0.05, 27 participant are required in this cross-over design. We will aim to recruit 35 patients to account for possible 20% dropout rate.

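### The secondary pregabalin-placebo comparison has no period term although sequence is what is randomised; the likely cost is lost precision, small unless drift between periods is large

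*Combined protocol and SAP*

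**What the plan says.** Section 2.4.1 randomises order: "the sequence of interventions will be determined: pregabalin and then matching placebo, or vice versa". Allocation is in blocks: "Randomization will be performed by blocks of 8 subjects, without stratification".

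For the treatment comparison, section 2.4.7 states "we will compare mean absolute pain reduction with pregabalin to absolute pain reduction to placebo", for both average and maximum daily pain, "using paired t-test, given normal data distribution". The fallback is: "If normal distribution is not obtained, we will use Wilcoxon signed ranked test". The section labels these analyses secondary, and they serve additional aim 1 in section 2.2. The primary analysis relates baseline MPT to percent pain reduction under each treatment: "The two slopes will be compared using t-test".

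None of these analyses includes period or sequence. The only mixed model in the plan is in section 2.4.9. It is a missing-data method for the primary outcome, used when more than 10% of those data are missing, and no period term is stated for it.

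**The concern.** In a two-period cross-over, a patient's pregabalin-minus-placebo difference holds the treatment effect and also the change between periods. The period part has one sign in patients who take pregabalin first and the opposite sign in those who take placebo first. A paired test treats all the differences as one sample. The period effect then counts as unexplained scatter and, if the two sequences contribute different numbers of completers, part of it stays in the estimate.

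The two outcome windows (days 24-28 of each phase) lie about six weeks apart, so some drift is possible, though the documents do not quantify it. At stake is the precision of the comparison that answers whether pregabalin relieves pain better than placebo, in a trial expecting about 28 completers.

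**Working it through.** **Plan's own figure.** Section 2.4.8 plans "to detect 0.3 (SD=0.5) difference in correlation coefficients between the two slopes", "with 85% power and alpha=0.05, 27 participant are required in this cross-over design". The ratio is 0.3/0.5 = 0.6. A paired t-test at two-sided 5% (the plan does not state sidedness) has 85.1% power with 27 patients and 83.6% with 26, so 27 reproduces. Recruiting 35 with 20% dropout leaves 35 × 0.8 = 28 completers.

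**Inputs for this check.** From the plan: 28 completers, blocks of 8, two-sided 5%. Assumed, because the documents give no figure: an SD of 2 NRS points for the within-patient difference, a treatment effect of 1.2 points, and pi from 0 to 1.5 points. The effect borrows the plan's ratio (0.6 × 2 = 1.2) for illustration only; that ratio was set for the slope comparison.

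**Model.** Let tau be the treatment effect, pi the period 2 minus period 1 effect on pain reduction, n1 the completers who took pregabalin first, n2 those who took placebo first, and n = n1 + n2. The expected within-patient difference is tau − pi in the first group and tau + pi in the second.

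- Shift in the plain paired estimate: pi(n2 − n1)/n.
- Variance seen by the paired test: about SD² + pi² × 4·n1·n2/n². At 14/14 this is SD² + pi².
- Period-adjusted estimate: the mean of the two sequence means, with standard error (SD/2)√(1/n1 + 1/n2) on n − 2 degrees of freedom. It does not depend on pi.

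**Equal sequences (14/14).** At pi = 1.0 the variance is 4 + 1 = 5, or 1.25-fold, so the interval is √1.25 = 1.12 times as wide. Adjusted power is exact: noncentrality 1.2/[(2/2)√(1/14 + 1/14)] = 3.17 on 26 degrees of freedom gives 86.3% at every pi. Simulated adjusted values of 86% or 87% are the same figure within simulation error. Simulation of the plain paired t-test gave:

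| pi (points) | Power, unadjusted | Power, adjusted | False positives, unadjusted |
|---|---|---|---|
| 0 | 86% | 86% | 5% |
| 0.25 | 86% | 86% | 5% |
| 0.5 | 85% | 86% | 4% |
| 1.0 | 80% | 86% | 3% |
| 1.5 | 72% | 86% | about 1.5% |

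The adjusted test rejects a true null about 5% of the time throughout.

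**Unequal sequences (16 and 12), pi = 1.0.** The shift is 1.0 × 4/28 = 0.14 point. The adjusted standard error is (2/2)√(1/16 + 1/12) = 0.38, so the shift is a little under 0.4 of a standard error. Unadjusted power is 69% if the imbalance works against pregabalin and 89% if it works in its favour; adjusted power is 86% either way. The unadjusted false-positive rate is about 4%.

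**How often sequences are that unequal.** With 35 patients in blocks of 8, the worst split at randomisation is 19:16, a shift of 3/35 = 9% of pi. If 28 complete and dropout is random, an imbalance of 4 or more arises in about 25% of trials. That counts both directions, so the unfavourable one has about 25/2 = 12.5%.

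**Slope comparison.** An additive period effect also adds scatter when the within-patient difference is regressed on MPT. In an illustrative simulation at 14/14, the sampling SD of the slope was 0.449 without a sequence term and 0.412 with it at pi = 1.0 (9% larger). At pi = 0 it was 0.396 and 0.405, so the term costs about 2%. This used absolute differences; the plan's slope is on percent reduction, for which no drift figure is available.

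The signed-rank fallback pools the sequences in the same way but was not simulated.

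**The case against.** The comparison is secondary, in a trial that section 2.4.1 calls a pilot. The loss becomes material only when drift approaches the drug effect: 1.0 to 1.5 points is 83% to 125% of the assumed 1.2, while at 0.5 point or less the power lost is about one percentage point. Patients must have had pain for more than two months, and background antidepressants and around-the-clock opioids must be stable. Blocking limits the imbalance. All of this stands, and it keeps the point modest.

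Three stronger readings are tempting, and the documents do not support them.

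- **That the plain test inflates false positives.** It does the reverse in every case with drift examined here.
- **That measuring both periods from one pre-study baseline creates drift.** A common baseline cancels in the paired absolute difference. Regression to the mean after entry at pain above 3 may also largely cancel, because both windows come more than three weeks after the start of treatment. A common baseline does not remove drift either. Pain is scored at the crossover visit (Table 1), but the analysis text does not say that score is used.
- **That the primary slope result is biased.** An additive period effect biases the slope difference only if baseline MPT differs between the randomised sequences; otherwise it adds noise.

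What the objection does not remove is that the omission is real and the remedy costs almost nothing even without drift.

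**Conclusion.** The omission is confirmed, and its consequence is mainly lost precision in a secondary analysis. Under the stated assumptions, power falls by about one point or less for drift up to 0.5 NRS point, from 86% to 80% at 1.0 and from 86% to 72% at 1.5. The shift in the estimate depends on the imbalance that happens to occur among completers, can go either way, and averages to zero over randomisation as long as dropout is unrelated to sequence. A reader might infer a systematic error for or against pregabalin; nothing in the plan supports that.

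The algebra is certain. The size is not, because it rests on pi and the SD, neither of which the documents give. This is a cheap improvement worth making, not a flaw that invalidates the trial.

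**What to change.** Before unblinding, amend section 2.4.7 as follows.

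1. Replace the paired t-test with a model containing treatment and period as fixed effects and a patient effect. For patients with data in both periods, this is the same as a two-sample t-test of period differences between the two sequences.
2. Replace the signed-rank fallback with a rank-sum test on period differences between sequences.
3. Add a period term to the slope model (a sequence term, if within-patient differences are regressed on MPT).
4. State which patients enter the model. A random patient effect also uses patients with only one period, and section 3.2 makes such patients possible, so this choice changes the analysis set. It should be reconciled with section 2.4.9.

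No carry-over pre-test is needed. The cost is one degree of freedom and SAP wording, with no new data, visits or patients. With no drift at all, power at 14/14 goes from 86.4% to 86.3%.

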	
 2. Spontaneous pain at baseline on 0-10 Numerical Rating Scale (NRS); 3. Assessment of pain symptoms on Neuropathic Pain Symptom Inventory (NPSI) and Brief Pain Inventory (BPI). 4. Assessment of mood on Depression, Anxiety and Positive Outlook Scale (DAPOS), and assessment of sleep on MOS Sleep Problem Index (SPI) scale. 5. Intraepidermal nerve fiber density and length of a 3-mm skin punch biopsy. 
Testing for intervention response (repetitive testing):
 
 1. Daily average and maximum pain intensity recording on 0-10 NRS; 2. Scoring of NPSI, BPI, DAPOS and SPI questionnaires at the end of week 4
Statistical Methodology	
The primary outcome is the comparison of slopes of the two correlations: baseline MPT vs % pain reduction with pregabalin, and baseline MPT vs % pain reduction with placebo. The two slopes will be compared using t-test. Significant difference between slopes will indicate that baseline MPT correlates with pregabalin response (vs. placebo response) in painful CIPN.
 
As secondary analyses, we will compare mean absolute pain reduction with pregabalin to absolute pain reduction to placebo (both for average daily pain and maximum daily pain), using paired t-test, given normal data distribution. If normal distribution is not obtained, we will use Wilcoxon signed ranked test.
 
In addition, we will perform Fisher exact test to compare the proportion of patients with 50% or more reduction in average pain intensity from baseline with pregabalin vs. placebo. Number needed to treat (NNT) will be calculated from this proportion of responders to pregabalin and placebo.

Table of Contents

1. SYNOPSIS	2
2. STUDY PROTOCOL	6
2.1 Background and Significance	6
2.2 Objective.....	8
2.3 Patient Selection	8
2.3.1 Inclusion Criteria	8
2.3.2 Exclusion Criteria	8
2.4 Design and Procedures.....	9
2.4.1 Study Design.....	9
2.4.2 Pre-Study Period	10
2.4.3 Study Period.....	11
2.4.4 Minimization of Bias	14
2.4.5 Observations and Measurements	15
2.4.6 QST protocol.....	15
2.4.7 Statistical Methods.....	17
2.4.8 Sample Size.....	18
2.4.9. Dealing with missing data.....	18
2.4.10 Clinical Procedures and Laboratory Tests	18
2.4.11 Drug procurement and storage.....	19
3.0 MANAGEMENT OF INTERCURRENT EVENTS	19
3.1 Adverse Experiences.....	19
3.2 Premature Discontinuation	21
3.3 Potential Risks	21
3.4 Procedures to Minimize Potential Risks.....	22

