2.4.4 Minimization of Bias

There will be no specific sex, ethnic or racial background for enrollment. Placebo arm is introduced to increase the ability to differentiate between the pharmacologic effects of pregabalin and

other possible effects. The study is designed as a cross-over in order to minimize inter-subject variability. The investigators and the subjects will be blinded to treatment allocation sequence.

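### Responder rates from the same patients on pregabalin and placebo are compared with Fisher's exact test, which assumes independent groups

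*Combined protocol and SAP*

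**What the plan says.** Section 2.4.1 randomizes each patient to an order of treatments: "the sequence of interventions will be determined: pregabalin and then matching placebo, or vice versa". Section 2.4.4 gives the reason for the design: "The study is designed as a cross-over in order to minimize inter-subject variability".

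For the responder endpoint, section 2.4.7 states "we will perform Fisher exact test to compare the proportion of patients with 50% or more reduction in average pain intensity from baseline", pregabalin against placebo. The synopsis repeats it: "we will perform Fisher exact test to compare the proportion of patients with 50% or more reduction". The section continues: "Number needed to treat (NNT) will be calculated from this proportion of responders to pregabalin and placebo".

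Just before this, the same paragraph compares mean absolute pain reduction "using paired t-test, given normal data distribution", with the Wilcoxon signed rank test as fallback. It then gives the purpose of the whole set: "These secondary analyses are aimed at detecting group differences in response to pregabalin vs. placebo".

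No McNemar test, conditional logistic model or other paired method for binary data appears anywhere. Nothing limits the Fisher test to the first period, or to a table of sequence by preferred period, where it could be valid.

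**The concern.** A treatment-by-response Fisher table enters about 28 to 35 patients as 56 to 70 independent observations. The observed difference in proportions is correct, since it equals the difference between the two discordant counts divided by n. The reference distribution is wrong, because it ignores the covariance between a patient's two outcomes.

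That covariance is probably positive. Patients differ in how readily they report improvement. As sections 2.4.2 and 2.4.7 read, both percentage reductions also share one screening baseline. In that case Fisher's p-values are too large, and a real drug effect is more easily reported as non-significant. With negative covariance the error goes the other way.

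At stake is the secondary efficacy result that clinicians read most easily, and the test that accompanies the NNT. It serves the first additional aim in section 2.2, whether pregabalin relieves pain better than placebo.

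**Working it through.** **1. The plan's own sample size treats the data as paired.** Section 2.4.8 sets out "to detect 0.3 (SD=0.5) difference in correlation coefficients between the two slopes" with 85% power and alpha 0.05, and states 27 participants. Taking alpha as two-sided:

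- Normal approximation: n = (1.960 + 1.036)² × (0.5/0.3)² = 24.9, so 25.
- Paired (one-sample) t-test with the noncentral t: n = 27, power 85.1%. This reproduces the stated figure.
- Two independent groups would need 50 per arm.
- Dropout: 27/(1 − 0.20) = 33.75, so 34, against 35 stated. With 20% loss, 35 × 0.8 = 28 complete.

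No sample size is given for the responder comparison.

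**2. What Fisher leaves out.** Let p1 and p0 be the responder probabilities on pregabalin and placebo, q = 1 − p, and phi the within-patient correlation.

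- Independent groups: Var = (p1q1 + p0q0)/n
- Paired: Var = (p1q1 + p0q0 − 2·phi·√(p1q1p0q0))/n

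With p1 = 0.40 and p0 = 0.15, the independent numerator is 0.24 + 0.1275 = 0.3675, and √(0.24 × 0.1275) = 0.175.

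- phi 0.3: 0.3675 − 0.105 = 0.2625, which is 71% of the independent value.
- phi 0.5: 0.3675 − 0.175 = 0.1925, which is 52%.

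**3. Two illustrative tables (assumed counts).**

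| n | Both | Pregabalin only | Placebo only | Neither | Fisher p | Exact McNemar p |
|---|---|---|---|---|---|---|
| 28 | 4 | 6 | 0 | 18 | 0.121 | 2 × (1/2)⁶ = 0.031 |
| 35 | 5 | 9 | 1 | 20 | 0.063 | 2 × (1 + 10)/2¹⁰ = 0.021 |

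The first table has the largest overlap that its totals (10 and 4 of 28) allow, with phi 0.55. If 3, 2, 1 or 0 placebo responders also respond on pregabalin, exact McNemar gives 0.070, 0.109, 0.146 or 0.180. Fisher gives 0.121 throughout, because it cannot see the overlap.

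**4. Power and type I error.** These come from exact enumeration of all paired tables, with P(both) = p1p0 + phi·√(p1q1p0q0) and rejection at two-sided 0.05. Rates and phi are assumptions. Section 2.1 gives NNTs of 4 to 7 for most drugs in neuropathic pain and 7.7 for pregabalin. A 40% v 15% contrast is NNT 1/0.25 = 4; 35% v 22% is 1/0.13 = 7.7.

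| n | Rates | phi | Fisher | Exact McNemar | Mid-p McNemar |
|---|---|---|---|---|---|
| 28 | 40% v 15% | −0.2 | 45.9% | 37.4% | 46.5% |
| 28 | 40% v 15% | 0 | 45.4% | 42.9% | 52.6% |
| 28 | 40% v 15% | 0.1 | 45.1% | 46.6% | 56.8% |
| 28 | 40% v 15% | 0.3 | 44.0% | 56.9% | 68.2% |
| 28 | 40% v 15% | 0.5 | 42.1% | 72.2% | 84.9% |
| 35 | 40% v 15% | 0.3 | 57.6% | 71.1% | 79.4% |
| 28 | 35% v 22% | 0 | 12.5% | 11.4% | 16.6% |
| 28 | 35% v 22% | 0.3 | 8.4% | 13.8% | 21.0% |
| 28 | 20% v 20% (type I) | 0 | 2.0% | 2.1% | 4.0% |
| 28 | 20% v 20% (type I) | 0.3 | 0.6% | 1.4% | 3.3% |
| 28 | 20% v 20% (type I) | 0.5 | 0.14% | 0.7% | 2.1% |

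With negative correlation, n = 28 and both rates 30%, Fisher's type I error is 4.4% at phi −0.2, 5.3% at −0.3 and 6.3% at −0.4.

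**The case against.** The case for leaving this alone, or ranking it low, has several parts.

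- **The analysis is secondary, in a study the protocol calls a pilot.** The primary slope comparison and the sample size do not use it, and the paired tests on mean pain already address pregabalin against placebo. This stands and limits the consequences.
- **With positive correlation the error is conservative.** It adds no false positives. This also stands: the practical harm is lost power. Inflation above 5% appeared only at phi of −0.3 or lower, which is implausible here.
- **The gain depends on assumed values.** At phi 0.1 exact McNemar is less than two points ahead. At phi 0 or below Fisher is slightly ahead of it. At the pregabalin NNT of 7.7 neither test has useful power with 28 patients. All true, and the n = 28 example table is the extreme one for its totals. But mid-p McNemar has more power than Fisher in every case examined with phi of 0 or above.
- **The NNT point estimate does not depend on pairing, and no NNT interval is planned.** Correct. The point matters only if an interval is added, which would be advisable.

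None of this supports Fisher's test for these data. No reason for choosing it is given, and it departs from the paired treatment of the continuous outcome in the same paragraph.

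**Conclusion.** The concern holds. Fisher's exact test, as specified, does not fit paired responder data, and its p-value is miscalibrated whenever a patient's two outcomes are correlated. If responder rates are near 40% and 15% and phi is 0.3 to 0.5, the choice costs about 13 to 30 points of power against exact McNemar with 28 completers, and more against mid-p. The true type I error falls well below 1% (both rates 20%). If phi is near zero, the two exact tests perform about equally. The direction rests on positive correlation, which the design rationale implies but the documents do not quantify. The primary conclusion and the NNT point estimate for a given set of patients are untouched.

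**What to change.** Replace the Fisher sentence in section 2.4.7 and the synopsis along these lines: *Responder status on pregabalin and on placebo will be cross-classified within patient and compared by the mid-p (or exact) McNemar test. The paired risk difference will be reported with a confidence interval for paired proportions, and the NNT and its interval will be derived from it.*

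If a period effect is a concern, specify instead the Mainland-Gart test or conditional logistic regression with a period term. Fisher's test can be kept within the Mainland-Gart approach, where the table is sequence by preferred period among discordant patients.

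Add a rule for patients with only one evaluable period. McNemar's test drops them, section 2.4.8 expects up to 20% dropout, and section 3.2 lets a patient stop the first treatment phase and still enter the second.

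The cost is a short wording change in two places, with no new data and no burden on patients. Make it before unblinding, since a change of test after results are seen would look data-driven.
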